3.0 Inclusion and Exclusion Criteria

3.1 Describe the criteria that define who will be included or excluded in your final study sample.

Fifty-two lung cancer survivors with sleep continuity disturbance will be recruited over 2 years. Eligibility criteria include the following: age >21 , stage I-III, non-small cell lung cancer, ≥ 6 weeks and ≤ 3 years post-surgical resection who are medically and psychiatrically stable. Subjects must be able to give consent. An NCI-designated comprehensive cancer center with a well-established thoracic surgery practice will be the recruitment site. A collaborative recruitment arrangement in the past has resulted in successful recruitment goal achievement.

3.2 Describe how individuals will be screened for eligibility.

The PI or research assistant (RA) will screen all eligible participants for sleep apnea using the ApneaLink device. Participants who screen positive for sleep apnea will receive 2 printed reports of the ApneaLink results: one for themselves and a copy for their provider, who will be advised to refer the participant for further sleep evaluation. Following a negative screen for sleep apnea, participants will be evaluated for sleep continuity disturbance through the use of Insomnia Severity Index, Epworth Sleepiness Scale and 14-day sleep diaries. Participants will also be screened for circadian activity rhythm disturbance with 14-day actigraphy and Morningness-Eveningness Questionnaire. A folder will be provided with each of the pretreatment instruments to complete and an actigraph to wear 24/7 at home. Following completion of pretreatment measures, participants will be randomized using a random number assignment to either red-yellow (control dim light) versus blue-green (experimental bright light) directed light therapy. Participants will be trained on how to wear the directed light therapy for 60-minutes within 30-minutes upon awakening for 1-week (Redd et al., 2014).

3.3 *Indicate specifically whether you will include or exclude each of the following special populations: (You may not include members of these populations as subjects in your research unless you indicate this in your inclusion criteria.)*

- *Adults unable to consent*
- *Individuals who are not yet adults (infants, children, teenagers)*
- *Pregnant women*
- *Prisoners*

These populations will not be included in the study.

3.4 *Indicate whether you will include non-English speaking individuals. Provide justification if you will exclude non-English speaking individuals.*

(In order to meet one of the primary ethical principles of equitable selection of subjects, non-English speaking individuals may not be routinely excluded from research. In cases where the research is of therapeutic intent or is designed to investigate areas that would necessarily require certain populations who may not speak English, the researcher is required to make efforts to recruit and include non-English speaking individuals. However, there are studies in which it would be reasonable to limit subjects to those who speak English: e.g., pilot studies, small unfunded studies with validated instruments not available in other languages, numerous questionnaires, and some non-therapeutic studies which offer no direct benefit.)

Non-English speakers will not be included in the study because this is a pilot study.

4.0 Study-Wide Number of Subjects (Multisite/Multicenter Only)

4.1 *If this is a multicenter study, indicate the total number of subjects to be accrued across all sites.*

This is not a multicenter study.

5.0 Study-Wide Recruitment Methods (Multisite/Multicenter Only)

If this is a multicenter study and subjects will be recruited by methods not under the control of the local site (e.g., call centers, national advertisements) describe those methods. Local recruitment methods are described later in the protocol.

5.1 *Describe when, where, and how potential subjects will be recruited.*

Response: NA

5.2 *Describe the methods that will be used to identify potential subjects.*

Response: NA

5.3 *Describe materials that will be used to recruit subjects. (Attach copies of these documents with the application. For advertisements, attach the final copy of printed advertisements. When advertisements are taped for broadcast, attach the final audio/video tape. You may submit the wording of the advertisement prior to taping to preclude re-taping because of inappropriate wording, provided the IRB reviews the final audio/video tape.)*

Response: NA

6.0 Multi-Site Research (Multisite/Multicenter Only)

6.1 *If this is a multi-site study where you are the lead investigator, describe the processes to ensure communication among sites, such as:*

- *All sites have the most current version of the protocol, consent document, and HIPAA authorization.*
- *All required approvals have been obtained at each site (including approval by the site's IRB of record).*
- *All modifications have been communicated to sites, and approved (including approval by the site's IRB of record) before the modification is implemented.*
- *All engaged participating sites will safeguard data as required by local information security policies.*
- *All local site investigators conduct the study appropriately.*

- *All non-compliance with the study protocol or applicable requirements will be reported in accordance with local policy.*

Response: NA

6.2 *Describe the method for communicating to engaged participating sites:*

- *Problems.*
- *Interim results.*
- *The closure of a study*

Response: NA

7.0 Study Timelines

7.1 *Describe the duration of an individual subject's participation in the study.*

Subjects will be expected to participate for approximately 10 weeks during which ApneaLink screening, completion of pre-intervention data collection, 1 week for intervention, and completion of post-intervention data collection will occur.

7.2 *Describe the duration anticipated to enroll all study subjects.*

Approximately 18 months.

7.3 *Describe the estimated date for the investigators to complete this study (complete primary analyses)*

December, 2017.

8.0 Study Endpoints

8.1 *Describe the primary and secondary study endpoints.*

The primary endpoint is whether subjects have a significant improvement in self-reported fatigue, sleep and circadian rhythms with the bright light intervention as compared to the dim light intervention. The secondary endpoint is to determine whether pre-treatment subjects with circadian dysrhythmia (circadian phase and amplitude abnormalities) will be significantly more likely to exhibit treatment responses than those who were not identified as having circadian dysrhythmia.

8.2 *Describe any primary or secondary safety endpoints.*

Response: It is expected that some patients with stage I-III NSCLC may experience periods of low oxygenation during sleep that may be identified during screening with the ApneaLink. We added a letter of referral to give to patients who may wish to alert their Providers about this finding.

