1.0 Objectives

- Assess the effect of morning bright light versus dim light therapy (control) on fatigue and sleep continuity disturbance in lung cancer survivors.
- Predict efficacy to morning bright light therapy versus dim light therapy (control) on fatigue and sleep continuity disturbance in lung cancer survivors.
- Evaluate, in a preliminary way, the extent to which time from treatment (as a proxy iatrogenic effects), sleep homeostatic “de-prime” (mismatch between sleep opportunity and ability), and circadian factors (phase and amplitude) predict illness severity and treatment response.

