1.1 Hypothesis

Hypothesis 1: Subjects in the Bright Light Treatment group will exhibit significant improvements as compared to Dim Light Treatment in fatigue, sleep and circadian activity rhythms.

Hypothesis 2: Subjects typed during baseline as having circadian dysrhythmia using actigraphy (circadian phase and amplitude abnormalities) will be significantly more likely to exhibit treatment responses.

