11.0 Data Management

11.1 Describe the data analysis plan, including any statistical procedures.

Hypothesis testing will be conducted using 2x2 ANOVAs for the first specific aim, with Logistic Regressions for the second specific aim (predicting treatment response and non-response) and with Linear and Logistic Regressions for the third specific aim (predicting illness severity and treatment response).

11.2 Provide a power analysis.

Response:

The primary outcome for sleep is the sleep efficiency score. Previous research has indicated that persons with satisfactory sleep have a sleep efficiency score exceeding 85, whereas persons reporting unsatisfactory sleep have a score at most 70, with both groups reporting a standard deviation of approximately 15. The estimated effect size from this study

is 1. The goal of this study is to improve sleep efficiency from an unsatisfactory level to a satisfactory level. Using a large effect size of .08 with a one-tailed significance of .025 and power of 80%, the required sample size for the two-group comparison is 26 per group for a total sample of 52.

11.3 Describe the steps that will be taken to secure the data (e.g., training, authorization of access, password protection, encryption, physical controls, certificates of confidentiality, and separation of identifiers and data) during storage, use, and transmission.

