12.0 Provisions to Monitor the Data and Ensure the Safety of Subjects

12.1 Describe the plan to periodically evaluate the data collected regarding both harms and benefits to determine whether subjects remain safe.

The PI will be responsible for ensuring data integrity and safety monitoring for human subjects and communicating any negative outcomes or any serious events to the IRBs and other offices/agencies. Because of the minimal to low risk associated with this protocol, the data safety and monitoring plan (DSMP) for this project involves close monitoring by the principal investigator (PI) and a safety officer, an Nurse Practitioner in the School of Nursing. The data safety monitoring team will ensure participant safety, ensure the validity and integrity of the data, monitor study progress, and make recommendations regarding appropriate protocol and operational changes which may have substantial effects upon the ultimate interpretation of the study. They will also be responsible for promptly report any serious adverse events to the Institutional Review Boards (IRB) at Roswell Park Cancer Institute, the VA Western New York Health Systems (VA WNYHS) and the University at Buffalo

Weekly reviews of participant accrual will be conducted by the PI during weekly research meetings. If participant accrual and/or retention drop below what is required for successful completion of this study, the PI will alert the statistician and strategies will be developed to overcome the identified problems. Records from subjects recruited during that week will also be scrutinized to insure that all participants are eligible for participation in the study. The PI and members of the research team will be monitoring developments in the literature and results of related studies that may have an impact on the safety of participants or on the ethics for the research study. Additionally, [name], a sleep research expert and consultant, will serve as a resource for new findings in the field and to assist with this clinical trial.

12.2 Describe what data are reviewed, including safety data, untoward events, and efficacy data.

Data review includes eligibility, referral for sleep apnea, referral for low oxygen during sleep, completion of data collection instruments, adherence to intervention, number of follow up phone calls accepted, and outcome measures of efficacy: fatigue, sleep and circadian activity rhythms. Daytime sleepiness will also be evaluated daily, but monitored weekly.

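### Fatigue, sleep and circadian rhythms are jointly primary, but the plan gives no rule for success across them, and its 80% power is for sleep efficiency alone

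*Combined protocol and SAP*

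**What the plan says.** Everything is in the combined protocol and SAP.

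- **Primary endpoint (8.1):** "The primary endpoint is whether subjects have a significant improvement in self-reported fatigue, sleep and circadian rhythms with the bright light intervention", compared with dim light.
- **Hypothesis 1 (1.1):** "Subjects in the Bright Light Treatment group will exhibit significant improvements as compared to Dim Light Treatment in fatigue, sleep and circadian activity rhythms". Section 12.2 lists the same three as "outcome measures of efficacy: fatigue, sleep and circadian activity rhythms".
- **Objective 1 (1.0):** "Assess the effect of morning bright light versus dim light therapy (control) on fatigue and sleep continuity disturbance in lung cancer survivors". Circadian rhythms are not named.
- **Analysis (11.1):** "Hypothesis testing will be conducted using 2x2 ANOVAs for the first specific aim". Nothing follows on how many domains must be significant, in what order, or at what level each.
- **Sizing (11.2):** "The primary outcome for sleep is the sleep efficiency score". From means of 85 and 70 and an SD of 15, "The estimated effect size from this study" is given as 1. The calculation then proceeds: "Using a large effect size of .08 with a one-tailed significance of .025 and power of 80" percent, giving 26 per group and 52 in total. No section gives an effect size or SD for fatigue or for any circadian measure.
- **Measures (9.2, 9.4, 9.5):** Fatigue is assigned to FACIT; the Brief Fatigue Inventory appears only in the instrument list. Sleep continuity is assigned to the Insomnia Severity Index, the diary and the Epworth scale, while sleep efficiency is listed as an actigraph output. Circadian rhythm is assigned to the actigraph and the Morningness-Eveningness Questionnaire (MEQ). The actigraph parameters are an open-ended list of mesor, amplitude and acrophase.
- **Status (2.1, 3.4, 9.1):** the study calls itself preliminary and a pilot.

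**The concern.** A primary endpoint with three components needs a stated rule, because the rule decides which error is at risk. Requiring all three protects alpha and costs power; accepting any one does the reverse. The plan states an alpha and a power as if there were one test, on one domain.

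A mixed result, such as sleep significant and fatigue not, has no defined interpretation. The success rule, the source of sleep efficiency and the circadian parameter could all be settled after the data are seen. The word self-reported in 8.1 adds to the doubt: it points sleep towards the diary and, if it extends to circadian rhythms, points those towards the MEQ rather than the actigraph.

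**Working it through.** **Inputs from the plan:** one-sided alpha .025, power 80%, 26 per group (11.2); effect size printed as .08, with 1 = (85 − 70)/15 derived just before it (11.2); 50 recruited and 40 completing (23.2).

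**Assumptions not in the plan:** effect sizes for fatigue and circadian rhythms; between-domain correlation r of 0, 0.5 or 0.9; pre-post correlation of 0.3 to 0.6; one variable per domain.

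**1. Reproduce 26 per group.** For a two-sample t-test, power comes from a noncentral t with 2n − 2 degrees of freedom and noncentrality d·√(n/2).
- d = 0.8: n = 25.52, so 26 per group. Power at 26 is 80.7%.
- d = 0.08, as printed: about 2,454 per group.
- d = 1: 17 per group. Power at 26 is 94.2%.

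The plan's figure reproduces only with 0.8.

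**2. The planned test.** For group-by-time in a pre-post model with equal variances, the effect on the change score is d/√(2(1 − ρ)). At d = 0.8 and 26 per arm:

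| Pre-post correlation ρ | Power |
|---|---|
| 0.3 | 67% |
| 0.5 | 80.7% |
| 0.6 | 89% |

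The two-sample figure therefore carries over only at ρ = 0.5. Steps 3 to 6 use the two-sample power.

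**3. All three required.** Joint power cannot exceed the power of any single component, so at the sizing value d = 0.8 it cannot exceed 80.7%. With equal d it is the trivariate normal probability that all three tests succeed. At r = 0 this is 0.8075³ = 0.527 for d = 0.8 and 0.9424³ = 0.837 for d = 1.

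| 26 analysed per arm | r = 0 | r = 0.5 | r = 0.9 |
|---|---|---|---|
| d = 0.8 in all domains | 53% | 62% | 73% |
| d = 1 in all domains | 84% | 87% | 91% |
| n per arm for 80% joint power, d = 0.8 | 38 | 35 | 31 |
| n per arm for 80% joint power, d = 1 | 25 | 23 | 20 |

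If the fatigue or circadian effect is smaller than the value in a power row, the figure falls below that row.

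**4. Any one suffices, unadjusted.** With no true effect in any domain, the one-sided error at r = 0 is 1 − 0.975³ = 7.3%. It is 6.3% at r = 0.5 and 4.2% at r = 0.9, against the stated 2.5%.

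**5. Any one suffices, with Holm.** The first step is .025/3 = .0083. Sleep efficiency alone (d = 0.8, 26 per arm) has 66% power at that level; 80% needs 35 per arm. The chance of at least one success is:

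| Effects | r = 0 | r = 0.5 | r = 0.9 |
|---|---|---|---|
| d = 0.8 in all three | 96% | 87% | 75% |
| d = 0.8 for sleep, 0.4 for the other two | 76% | 69% | 66% |

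At r = 0 the first entry is 1 − (1 − 0.658)³ = 0.960.

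**6. Fixed order, sleep then fatigue.** With d = 0.8 on both, the chance of passing both is 65% (0.8075² = 0.652), 70% or 76% at r = 0, 0.5 or 0.9.

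**7. Number analysed.** With 40 completers, 20 per arm, a single endpoint at d = 0.8 has 69% power.

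**The case against.** The best defence is that 8.1 and Hypothesis 1 join the domains with a plain conjunction, so all three must succeed and alpha needs no sharing. That is the more natural reading, and no section proposes that any one suffices. A reader might infer from the 7.3% that the plan inflates its type I error. The documents do not support that: the figure belongs to a rule that they leave open but nowhere adopt.

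Nor is a power shortfall shown. The only effect the plan derives from its own data is 1, and if that held in every domain, joint power at 26 per arm would be 84% to 91%. What stands is that the stated 80% is not the power of the endpoint in 8.1, whose power is unknown.

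The study is also a pilot, where formal gatekeeping is partly a matter of taste. That limits how much machinery to ask for. But the plan sets a formal alpha and power and defines success as significant improvement, so it needs a rule.

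The fatigue measure is not a real gap, since 9.2 assigns FACIT. A reader might also take 20 per arm as settled. It follows from 23.2, but 20.2 says that oversampling will deliver the target, so the sections conflict and the 69% is conditional.

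**Conclusion.** The point holds as a gap between the declared endpoint and the stated operating characteristics. Under all-three, alpha is held, and joint power at the sizing value d = 0.8 is capped at 80.7%: 53% to 73% with equal effects, less if the fatigue or circadian effect is smaller. Under any-of-three without adjustment, one-sided error is 4.2% to 7.3%, not 2.5%. The one-sided .025 and the 80% therefore cannot both be relied on for the primary endpoint under either rule without a further assumption, such as effects near 1 in all domains.

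These figures rest on 26 analysed per arm, .08 read as 0.8, one variable per domain, between-domain correlation of 0 to 0.9 and, for the planned group-by-time test, a pre-post correlation of 0.5. They do not show that the trial is underpowered, because the documents give no effect for two of the three domains. Nor can one infer that a Holm correction would come free of extra participants: that depends on the same unknown effects. The sponsor should settle this before data are seen.

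**What to change.** In 8.1, name one measure per domain: FACIT-Fatigue, sleep efficiency from one stated source (diary or actigraph), and one circadian parameter. Then adopt one rule and align Objective 1, Hypothesis 1 and 8.1 with it.

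- **(a) All three, each at one-sided .025.** In 11.2, label the 80% as the power for sleep efficiency only, and give the joint power with its assumptions. Cost: wording, unless 80% joint power is wanted, which at d = 0.8 needs 31 to 38 analysed per arm.
- **(b) One primary, the others in fixed order at .025.** Sleep efficiency is the outcome the trial was sized on, but 11.2 calls it primary only for sleep, so putting it first is the sponsor's choice. Cost: fatigue, listed first throughout, becomes conditional (65% to 76% chance of passing both at d = 0.8), and the circadian claim becomes conditional on both.
- **(c) Any of three with Holm.** State that sleep efficiency alone has 66% power at the first step with 26 per arm, and that the chance of at least one success depends on unknown effects elsewhere. Holding 80% for sleep efficiency at that step needs 35 per arm.

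Report all other scales, including the Brief Fatigue Inventory, as exploratory, with estimates and confidence intervals.

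In 11.2, correct .08 to 0.8 and state the pre-post correlation assumed. Also state the number analysed per arm, reconciling the 52 required (11.2), the oversampling statement (20.2) and the 50 recruited with 40 completing (23.2). These edits cost wording only. They do not themselves secure 80%, which still depends on the correlation and the number analysed.

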9.0 Procedures Involved

9.1 *Describe and explain the study design.*

This pilot study will include 52 lung cancer survivors using a 2X2 mixed model with Pre-Post assessments in two groups. Twenty-six participants will be randomized to red yellow directed light (control) and 26 participants will receive blue green (experimental) directed light therapy. The light source (Re-Timer) will be worn for 60-minutes every morning within 30-minutes upon awakening for 1-week. Participants will receive a weekly telephone call to ensure adherence to treatment plan and screen for safety/adverse events.

9.2 *Provide a description of all research procedures being performed and when they are performed, including procedures being performed to monitor subjects for safety or minimize risks.*

Screening for inclusion criteria includes a YES response to the following questions:

Are at least 21 years of age?

Do you have a diagnosis of non-small cell lung cancer stage I, II or III?

Have you had your lung cancer surgically removed at least 6 weeks ago, but not longer than 3 years ago?

Screening for exclusion criteria includes a NO response to the following questions:

Do you have any unmanaged medical or psychiatric diagnoses?

Are you currently pregnant?

Do you have a diagnosis of epilepsy?

Following informed consent, in order to rule-out sleep apnea as a confounder and assess for respiratory disturbance, all eligible participants will be screened for sleep apnea and hypoxia using the portable ApneaLink device for one night. Following a negative screen for sleep apnea, demographics, diagnoses, treatments, comorbidities, etc. will be recorded using the Demographics and Treatment Survey. Fatigue will be measured using the Functional Assessment of Chronic Illness Therapy Fatigue (FACIT) (Cella, Lai et al. 2011). Sleep continuity disturbance will be determined by Insomnia Severity Index (Bastien et al., 2001), 14-day sleep diary and the Epworth Sleepiness Scale (Johns 1991). Circadian activity rhythm disturbance will be assessed using the 14-day actigraph (Ambulatory Monitoring, Inc, Ardsley, NY) and Morningness-Eveningness Horne-Ostberg/Questionnaire (MEQ) (Horne and Ostberg 1976). Surveys and actigraphy will be performed at baseline and again after treatment ends. Expectation for treatment effectiveness will be assessed with the investigator developed Expectation Questionnaire before and

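### Hypothesis 2 and the secondary endpoint drop the dim-light comparator that Objective 2 names, and no arm-by-dysrhythmia term is stated, so a merely prognostic factor could be read as predicting benefit from bright light

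*Combined protocol and SAP*

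**What the plan says.** The second objective in section 1.0 is comparative: "Predict efficacy to morning bright light therapy versus dim light therapy (control) on fatigue and sleep continuity disturbance in lung cancer survivors". The primary endpoint in section 8.1 is comparative too; it asks about improvement "with the bright light intervention as compared to the dim light intervention".

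The secondary endpoint, in the next sentence of section 8.1, is not. It asks whether subjects with baseline circadian dysrhythmia "will be significantly more likely to exhibit treatment responses than those who were not identified as having circadian dysrhythmia". Hypothesis 2 in section 1.1 has the same shape: "Subjects typed during baseline as having circadian dysrhythmia using actigraphy (circadian phase and amplitude abnormalities) will be significantly more likely to exhibit treatment responses". Neither names an arm.

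For the analysis, section 11.1 offers one phrase per aim. For aim 2 it is "with Logistic Regressions for the second specific aim (predicting treatment response and non-response"; for aim 3 it is "with Linear and Logistic Regressions for the third specific aim (predicting illness severity and treatment response". It does not list model terms, say which arms enter, or define a responder or dysrhythmia. Section 11.2 sizes the trial on the bright-versus-dim comparison of sleep efficiency and gives no power for Hypothesis 2.

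**The concern.** Comparing response between subjects with and without dysrhythmia measures how dysrhythmia relates to outcome. Whether dysrhythmia changes the benefit of bright over dim light is a difference between two such comparisons, one in each arm. Only the second answers Objective 2.

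If dysrhythmic subjects respond more often whichever light they wear, the stated contrast can be significant with no differential benefit at all. The likely harm is a prognostic marker carried into the next trial as a selection criterion for bright light. The primary bright-versus-dim comparison is not affected.

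**Working it through.** **The plan's own figure.** Section 11.2 gives 26 per group for the two-group comparison. With effect size d = 0.8, one-sided 0.025 and 80% power, the normal formula gives n = 2(1.960 + 0.842)²/0.8² = 24.5, so 25. The t-based calculation gives 25.5, so 26. This reads the printed .08 as 0.8, which is a separate matter. There is no figure to reproduce for Hypothesis 2.

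**Inputs.** From the documents: 26 per arm (9.1), 40 completers (23.2), SD 15 (11.2). Assumed, because the documents give neither: response rates of 30% without and 60-70% with dysrhythmia, and prevalence 30-70%. Tests are at 5% two-sided.

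**Two worlds that the stated contrast cannot tell apart (response rates).**

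| | Bright, dysrhythmia | Bright, none | Dim, dysrhythmia | Dim, none |
|---|---|---|---|---|
| Prognostic only | 70% | 30% | 70% | 30% |
| True predictor | 70% | 30% | 30% | 30% |

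The bright arm is identical in both rows, so a bright-arm-only contrast cannot distinguish them. The pooled contrast is 70% vs 30% in the first row, but only (70 + 30)/2 = 50% vs 30% in the second. It therefore favours the world in which dysrhythmia does not predict benefit. The log odds ratio for dysrhythmia is ln[(0.7/0.3)/(0.3/0.7)] = 1.69 in each arm of the first row, so the interaction is zero there. In the second row the interaction is 1.69 - 0 = 1.69.

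**Hand check, prognostic-only world, even split.** Power ≈ Φ[(|p1 - p0| - 1.96·SE0)/SE1], where SE0 = √(2p̄(1 - p̄)/n), SE1 = √((p1(1 - p1) + p0(1 - p0))/n), and n is the number in each dysrhythmia group.
- Pooled, 40 completers (n = 20), 70% vs 30%: SE0 = 0.158, SE1 = 0.145, giving Φ(0.62) = 73%.
- Pooled, 40 completers, 60% vs 30%: SE0 = 0.157, SE1 = 0.150, giving Φ(-0.06) = 48%.
- Pooled, 52 subjects (n = 26), 70% vs 30%: SE0 = 0.139, SE1 = 0.127, giving Φ(1.01) = 84%.
- Bright arm only, 40 completers (n = 10), 70% vs 30%: SE0 = 0.224, SE1 = 0.205, giving Φ(-0.19) = 43%.

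**Simulation, prognostic-only world (20,000 trials per setting, prevalence 30-70%).** Percentage of trials significant:

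| Test | 40 completers | 52 subjects |
|---|---|---|
| Pooled contrast | about 43-73% | about 53-85% |
| Pooled with arm main effect | about 45-75% | about 56-87% |
| Bright arm only | about 26-44% | about 31-63% |

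Across both sample sizes the arm-by-dysrhythmia interaction is significant in about 2-3% of trials with a corrected Wald test and about 7-10% with a likelihood-ratio test. The spread reflects the choice of small-sample test. Adding an arm main effect does not help, because it leaves the dysrhythmia coefficient an average over arms.

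**Cost in power, true-predictor world, 40 completers.** The pooled contrast is significant in about 23-25% of trials and the interaction, calibrated to 5% size, in about 18-22%. Bright arm only gives about 41-45%, but it cannot tell the two worlds apart.

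**Precision of the interaction on a continuous outcome.** With 40 completers in four cells of 10, the unadjusted SE is √(4 × 1/10) = 0.632 SD, or 0.632 × 15 = 9.5 sleep-efficiency points. Power for a 0.8 SD interaction is about 23% (t, 36 df); 80% power needs about 1.8 SD.

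**The case against.** The strongest reply is that the intent is already there. Section 11.1 attaches the logistic regressions to the second aim, not to Hypothesis 2. If that aim is the second objective, it names the dim-light control, and nothing in 11.1 rules out an interaction. This stands. A reader might infer that the plan has chosen a pooled or single-arm analysis that ignores the control arm; the documents do not support that. What they show is an unspecified model, alongside a hypothesis and an endpoint worded without the comparator. That leaves the choice of contrast open until the data are seen.

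The rates above also need a strong prognostic effect, in the direction of Hypothesis 2, under dim light as well. The documents neither support nor exclude that, so the figures are illustrations and not forecasts.

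A reader might also infer that regression to the mean alone would produce false positives. With no treatment effect, 40 completers and response defined as an improvement of at least 0.5 SD, the rate favouring dysrhythmic subjects was mostly about 2.5-7%, against a nominal 2.5% in that direction. It reached 5-16% only when the circadian measure was assumed to add nothing beyond the baseline score. This is a minor part of the case.

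Finally, this is a secondary endpoint in a pilot, and the repaired test will seldom give a firm answer. That is true, and it limits the weight of the point, but it does not make the stated contrast answer Objective 2.

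**Conclusion.** The point holds as a gap between aim, endpoint and analysis, and should be fixed. Objective 2 needs the dim-light arm; Hypothesis 2 and the secondary endpoint do not use it, and section 11.1 does not state the term that would. Under the assumed rates, a factor with no bearing on the benefit of bright light makes the pooled contrast significant in about 43-73% of trials at 40 completers and 53-85% at 52. The exact percentages depend on those assumptions. That the stated contrast cannot separate prognosis from prediction does not.

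The documents do not show that a wrong analysis has been chosen, and the finding does not reach the primary comparison.

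**What to change.** In sections 8.1 and 11.1, state that Hypothesis 2 is tested by the arm-by-baseline-dysrhythmia interaction in all randomised subjects with outcome data. The model should include arm and dysrhythmia main effects and the baseline value of the outcome. Fix the outcome, the responder rule and the dysrhythmia definition before outcome data are analysed. That is the workable milestone, since the documents describe no blinding. Sleep efficiency is one candidate outcome, given the aim in 11.2: "The goal of this study is to improve sleep efficiency from an unsatisfactory level to a satisfactory level". Report the interaction with its 95% CI, label it exploratory, and use the same form for the treatment-response part of aim 3. A linear model of the post-treatment score with continuous phase and amplitude is an option, not a requirement.

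The cost is wording. Section 9.2 already provides the data: "Surveys and actigraphy will be performed at baseline and again after treatment ends". Section 9.4 lists amplitude and acrophase among the actigraph outputs. No visits, subjects or measurements are added. The price is low precision and a modest loss of power against the pooled contrast for a true predictor. If a logistic interaction is kept, name the small-sample test, because its error rate depends on that choice.
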